15.3.3.6. Definition of Severity of Adverse Events (AEs)

Severity of any AE will be recorded in the CRF.

Severity of any AE will be graded according to the National Cancer Institute - Common Terminology Criteria for Adverse Event (NCI-CTCAE) (Version 4.03) as reported in Table 15-2.

Table 15-2: Definition of Severity of Adverse Events (AEs)

Grade 1	Mild; asymptomatic or mild symptoms; clinical or diagnostic observations only; intervention not indicated.
Grade 2	Moderate; minimal, local or non-invasive intervention indicated; limiting age-appropriate instrumental ADL*.
Grade 3	Severe or medically significant but not immediately life-threatening; hospitalization or prolongation of hospitalization indicated; disabling; limiting self-care ADL**.
Grade 4	Life-threatening consequences; urgent intervention indicated.
Grade 5	Death related to AE.

[figure not shown]
National Cancer Institute - Common Terminology Criteria for Adverse Event (NCI-CTCAE) Version 4.03 A Semi-colon indicates 'or' within the description of the grade.

ADL: Activities of daily living

Note the distinction between serious and severe AEs: **Severe** is a measure of intensity whereas an event must meet one of the criteria for serious events listed in Section 15.3.3.6 to be considered **serious**; thus, a **severe** reaction is not necessarily a **serious** reaction. For example, a headache may be severe in intensity, but would not be classified as serious unless it met one of the criteria for serious events listed in Section 15.3.3.6. An AE that is assessed as Grade 3 (severe) or Grade 4 (potentially life-threatening) should not be confused with a SAE.

15.3.3.7. Serious Adverse Event (SAE) Reporting Procedure for Investigators to Regulis

The Investigator must report (by fax, telephone or email) all initial and follow-up SAE and pregnancy reports to Regulis' Pharmacovigilance Department within 24 hours of awareness of an SAE.

^{*}Instrumental ADL refer to preparing meals, shopping for groceries or clothes, using the telephone, managing money, etc.

^{**}Self-care ADL refer to bathing, dressing and undressing, feeding self, using the toilet, taking medications, and not bedridden.

If, for any reason, it is not possible to complete all sections of the SAE form within 24 hours, transmission of the form must not be delayed and the outstanding information should be sent on a follow-up SAE form.

If the SAE is reported by telephone, all points on the SAE form should be covered in the initial telephone report and followed by a completed and signed SAE form to verify the verbal information given previously. In addition, the event must be documented in the CRF.

Blank copies of the SAE forms are included in the Investigator Site File.

The SAE form must be completed as fully as possible with information relevant to the SAE(s) being reported. All fields should be populated or marked accordingly if no information is available.

Copies of relevant Case Report Form (CRF) pages, such as concomitant medications and medical history may be sent as attachments to the SAE forms.

Death and life threatening SAEs must be reported by the Investigator to the Medical Monitor immediately by phone on [name] or [name] (out of hours the main reception will contact 'first call' who will take a message and contact the medical monitor if they are unavailable by mobile). The SAE Form must then be e-mailed or faxed to Regulis Safety Department as above.

All incidents of pregnancy (of the patient or patient's partner) during the study must be reported and follow-up of the pregnancy outcome must be made. Specific pregnancy forms should be completed.

15.3.3.8. Follow-up SAE Reports

For all SAEs where important or relevant information is missing, active follow-up should be undertaken. Investigators or other site personnel should inform Regulis of any follow-up information on a previously reported SAE immediately but no later than 24 hours after they become aware of the SAE. The follow-up information must be presented on an SAE form marked as follow-up. It is necessary only to provide the new information, with the SAE form signed by an Investigator.

Investigators or other site personnel should send relevant or requested anonymized supporting documentation (e.g. ECG, laboratory results, autopsy report) to Regulis.

The Investigator will ensure that all the necessary information is provided within the timelines stipulated by Regulis when the request for information is made.

Follow-up reports (as many as required) should be completed and faxed following the same procedure above.

15.3.3.9. Reporting Serious Adverse Events (SAEs) to Independent Ethics Committee(s) (IEC[s])/ Institutional Review Board(s) (IRB[s])/ Regulatory Authorities (RA[s])

The Sponsor is responsible for informing local IEC(s)/IRB(s)/RA(s) of the applicable safety reports in compliance with local regulations. Copies of all correspondence relating to reporting of any safety reports to the IEC/IRB/RA[s] should be maintained in the Investigator Site File and provided to Orion.

With respect to SUSARs, the reference document for definition of expectedness is the Package Insert of ProvayBlueTM (refer to APPENDIX 1: US Package Insert of ProvayBlueTM).

The Sponsor, or its designee, Orion, will inform Investigators, central IEC(s)/IRB(s) and RAs of applicable safety reports, as required.

16. EVALUATION OF RESULTS

16.1. SAMPLE SIZE AND STUDY POWER

Because this is an ultra-orphan indication, the enrollment will be 10 patients, in adult and pediatric population.

Based on evaluation of historical data, the potential enrollment for this study is estimated to be 1/3 patient per site per year (i.e., one patient per site over the study period of approximately 32 months). Thus it is expected that 10 patients may be enrolled during the 3-year study.

A sample size of 10 will provide at least 80% power to detect a 90% response rate and exclude a response rate less than 50%.

As this is an open label study with only one treatment there will be no randomization and no blinding of subjects. Study numbers will be allocated to subjects in the order in which they are enrolled into the study.

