Based on evaluation of historical data, the potential enrollment for this study is estimated to be 1/3 patient per site per year (i.e., one patient per site over the study period of approximately 32 months). Thus it is expected that 10 patients may be enrolled during the 32-months-study.

A sample size of 10 will provide at least 80% power to detect a 90% response rate and exclude a response rate less than 50%.

As this is an open label study with only one treatment there will be no randomization and no blinding of subjects. Study numbers will be allocated to subjects in the order in which they are enrolled into the study and by site.

Number of planned visits:

The trial includes the following visits:

- Screening and enrolment
- Study Treatment
 - H0: ProvayBlueTM Dose 1
 - H1: 1 hour after the end of ProvayBlueTM infusion. Administration of ProvayBlueTM Dose 2 (if applicable)
 - H2: 2 hours after the end of ProvayBlueTM Dose 1 infusion
 - H3: 2 hours after the end of ProvayBlueTM Dose 2 infusion (if applicable)
- H24 (24 hours after the end of ProvayBlueTM Dose 1 infusion)
- Hospital Discharge (if earlier than H24)
- Follow up visit (5 -10 days following the last ProvayBlueTM administration)
- Follow up call (10 -15 days following the last ProvayBlueTM administration)

Efficacy parameters:

The following efficacy parameters will be assessed:

• A reduction in metHb by 50% within 1 hour of dosing;

- Concomitant normalization of respiratory rate within 2 hours of the first dose of ProvayBlueTM;
- Concomitant normalization of heart rate within 2 hours of the first dose of ProvayBlueTM;
- Concomitant normalization of diastolic blood pressure (DBP) within 2 hours of the first dose of ProvayBlueTM;
- Concomitant normalization of systolic blood pressure (SBP) within 2 hours of the first dose of ProvayBlueTM.

Pharmacokinetic parameters:

• PK samples will be analyzed for methylene blue and azure B.

PK samples are to be taken at the discretion of the Investigator based on the condition of the patient. The time blood sample(s) are taken should be recorded, but there is no absolute time window for the PK samples. Suggested PK sampling time points are as follows:

- Approximately 1 hour after the end of each ProvayBlueTM infusion (i.e. Dose 1, Dose 2 and any additional dose if applicable);
- Prior to Dose 2 ProvayBlueTM infusion (if applicable);

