6.5. PROVAYBLUETM

ProvayBlueTM is an oxidation-reduction agent indicated for the treatment of pediatric and adult patients with acquired methemoglobinemia (refer to APPENDIX 1: US Package Insert of ProvayBlueTM).

Methylene blue is a water soluble thiazine dye that promotes a non-enzymatic redox conversion of metHb to hemoglobin. *In situ*, methylene blue is first converted to leucomethylene blue (LMB) via nicotinamide adenine dinucleotide phosphate (NADPH) reductase. It is the LMB molecule which then reduces the ferric iron of metHb to the ferrous state of normal hemoglobin.

The efficacy of ProvayBlueTM was assessed on the basis of a metHb decrease of at least 50% within 1 hour after intravenous (IV) administration of 1–2 mg/kg ProvayBlueTM (or a bioequivalent formulation) in 6 patients identified by retrospective chart review or literature search. All 6 patients had a decrease in metHb by at least 50% within 1 hour after treatment.

An additional 41 cases of treatment of methemoglobinemia with a methylene blue class product were identified in the published literature. Of these 41 patients, 37 (90%) had a metHb decrease of at least 50% within 1 hour after intravenous administration of the methylene blue class product.

In a combined analysis of all 47 patients treated intravenously with ProvayBlueTM (or a bioequivalent formulation) or with another methylene blue class product, there was no difference in response rate by dose. The metHb decreased by at least 50% within 1 hour of infusion for 15/17 (88%) of patients treated with 1 mg/kg, 12/13 (92%) treated with 2 mg/kg and 16/17 (94%) treated with a different dose or for those whose dose was not reported.

Refer to APPENDIX 1: US Package Insert of ProvayBlueTM for adverse reactions, clinical pharmacology and non-clinical toxicology information associate with ProvayBlueTM.

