16.2.1. General Considerations

Continuous variables will be summarized by descriptive statistics (number of patients, mean, standard deviation [SD], minimum, median and maximum). Geometric mean and coefficient of variation (CV) will be presented for PK parameters when appropriate. Categorical data will be summarized by absolute and relative frequencies.

A 95% confidence interval (CI) for the responder rate will be presented for each of the primary and secondary endpoints.

All variables will be listed on a patient level.

Unless indicated otherwise, summary statistics will be reported for observed data only. Missing data will not be imputed. If a baseline value is missing, no change from baseline will be calculated.

Baseline for all assessments will be defined as the last measurement taken prior to dosing with study drug.

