16.4. EVALUATION OF EFFICACY

Refer to Sections 7.2.1 and 7.2.2 for the primary and secondary efficacy endpoints, respectively.

Efficacy evaluations will be performed using the FAS.

Efficacy will be assessed based on the metHb level and on the normalization of respiratory rate, heart rate and blood pressure after administration of ProvayBlueTM (single- or repeat dose).

The results will be descriptive only. A 95% CI for the responder rate will be presented for each of the primary and secondary endpoints. The results will be compared with historical methylene blue results to confirm that ProvayBlueTM's results are not unexpected.

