1. INTRODUCTION AND SCOPE

ProvayBlue™ (methylene blue) was approved under the accelerated approval regulation, 21 CFR 314.510. Provepharm was required to conduct “further adequate and well-controlled studies” to verify and describe the clinical safety and benefit of the agent in therapeutic use for the treatment of acquired methemoglobinemia. To fulfill this requirement, Provepharm has initiated 2 studies and enrollment to both studies are closed at this time.

The first study, protocol PVP-2016003, titled “Open Label Clinical Study to Evaluate the Safety and Efficacy of ProvayBlue™ (Methylene Blue) for the Treatment of Acquired Methemoglobinemia,” was initiated 19 October 2017; the study had enrolled a total of 7 patients when the enrollment was closed on 31 August 2020. This study is referred to hereafter as the Interventional Study. Because of the slow pace of enrollment in this study, doubtless due to the paucity of patients with this ultra-rare disease available for assessment, a stand-alone database, as commonly utilized with clinical trials, has not been setup to capture the data; rather, all clinical data were captured on a paper case report form (CRF).

The second study, protocol HQF-METHB-2018001, titled “Use of Methylene Blue in Acquired Methemoglobinemia: Prospective Observational Registry (metHb),” started May 2018, and enrolled 24 patients before closure on 31 August 2020. This study is referred to hereafter as the Observational Study. The Observational Study was expected to last 2 years after the commencement of enrollment in up to approximately 50 hospital systems. This Observational Study was designed to support low-burden screening and data collection, and to enroll real-world cases of acquired methemoglobinemia treated with ProvayBlue™ without restriction; thus, study sites were more amenable to participate in this program than in the Interventional Study. When enrollment was closed, approximately 90 individual hospitals were approved to enroll patients into the Observational Study; however, only 24 patients were enrolled, again owing to the rarity of the clinical presentation of interest. An electronic database has been set up to house data from both studies.

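### The 80% power stated for 10 patients cannot be reached by any exact responder rule with a true one-sided error of 5% or less; under the 9/10 rule it is 73.6%

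*Protocol*

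**What the plan says.** Protocol 16.1 justifies the sample size first by rarity and expected accrual. It then states that 10 patients give "at least 80% power to detect a 90% response rate and exclude a response rate less than 50" percent. The synopsis repeats it under Total sample size: "A sample size of 10 will provide at least 80% power to detect a 90% response rate". Neither place gives an alpha, a sidedness, a test, a CI method or the number of responders that would count as excluding 50%.

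The only confidence level in the protocol's statistical section is in 16.2.1: "A 95% confidence interval (CI) for the responder rate will be presented for each of the primary and secondary endpoints". No CI method is named there, and the interval is not linked to the power sentence. Section 16.4 adds: "The results will be descriptive only".

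The SAP (titled a Data Summary Plan) takes precedence over the protocol's statistical section where the two differ (SAP 1). SAP 3.4 plans no inferential testing and makes its 95% intervals two-sided where they are given. SAP 1 also reports that "the study had enrolled a total of 7 patients when the enrollment was closed on 31 August 2020".

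**The concern.** A power figure has meaning only with its error level and decision rule, and here both are missing. With 10 patients and a yes/no outcome only a few rules exist, and moving the threshold by one responder changes power and error by large steps. A normal-approximation figure can then be well off what the design delivers.

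At stake is what a reader of the protocol or study report would believe. The study answers a post-marketing requirement, and the sentence tells the reader that a drug with a true 90% response rate would fail to exclude 50% at most 20% of the time.

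**Working it through.** **Inputs.** n = 10, p1 = 0.90, p0 = 0.50, stated power at least 80% (Protocol 16.1). No dropout inflation is applied, because Protocol 9.5.2 lets recruitment rise until 10 patients are evaluable. Alpha is not stated, so one-sided 2.5% (two-sided 5%) and one-sided 5% are both shown. Historical response rates come from Protocol 6.5.

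**Step 1. Reproduce the stated figure.** The one-sample large-sample formula at two-sided 5% and 80% power gives

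n = [(1.96 × 0.5 + 0.8416 × 0.3) / 0.4]² = 9.49, rounded up to 10.

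At n = 10 the critical rate is 0.5 + 1.96 × √(0.25/10) = 0.810, and the approximate power is Φ[(0.9 − 0.810) / √(0.09/10)] = 82.9%. At one-sided 5% the critical rate is 0.760 and the approximate power 93.0%. So the claim does follow from a standard approximation. That the sponsor used this formula is an inference.

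**Step 2. Exact binomial, n = 10.** Error is P(X ≥ r) at a 50% rate; power is P(X ≥ r) at a 90% rate.

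| Rule | Error | Power |
|---|---|---|
| ≥ 7/10 | 17.19% | 98.7% |
| ≥ 8/10 | 5.47% (56/1024) | 93.0% |
| ≥ 9/10 | 1.07% (11/1024) | 73.6% |
| 10/10 | 0.10% | 34.9% |

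For ≥ 9/10, power = 10 × 0.9⁹ × 0.1 + 0.9¹⁰ = 0.3874 + 0.3487 = 0.7361.

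No row has both power of at least 80% and error of 5% or less. The conclusion is the same at one-sided 2.5%.

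**Step 3. Why the approximation misleads.** The two-sided 5% formula needs an observed rate of at least 0.810. Since 8/10 = 0.80 falls short, its rule is in fact ≥ 9/10, with 73.6% power and not 82.9%. The one-sided 5% version (0.760) accepts 8/10, so its power is real, but its true error is 5.47%.

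**Step 4. Using the planned 95% CI as the criterion.** Taking a two-sided 95% CI whose lower limit must exceed 50% is an inference, since the protocol does not make the link.

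| Method | Lower limit, 8/10 | Lower limit, 9/10 |
|---|---|---|
| Clopper-Pearson | 44.4% | 55.5% |
| Wilson | 49.0% | 59.6% |
| Agresti-Coull | 47.9% | 57.4% |
| Jeffreys | 49.7% | 61.9% |
| Wald | 55.2% | 71.4% |

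The first four need 9/10. Only Wald accepts 8/10, and its lower-tail error is then 5.47% against a nominal 2.5%.

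**Step 5. Sensitivity to the assumed rate, rule ≥ 9/10.**
- "15/17 (88%) of patients treated with 1 mg/kg": power 66.7%.
- "Of these 41 patients, 37 (90%) had a metHb decrease of at least 50% within 1 hour": power 74.6%.
- "In a combined analysis of all 47 patients", the three dose groups sum to (15 + 12 + 16)/(17 + 13 + 17) = 43/47: power 79.3%.

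The true rate must be at least 91.7% for ≥ 9/10 to have 80% power.

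**Step 6. Other sample sizes.** Exact power does not rise smoothly with n. With error of at most 2.5% per tail, the smallest n with 80% power at a 90% rate is 12 (≥ 10/12: 88.9% power, 1.93% error). At one-sided 5%, n = 8 (≥ 7/8: 81.3%, 3.52%) and n = 11 (≥ 9/11: 91.0%, 3.27%) both work, while n = 10 does not. With the 7 patients this study enrolled, the exact two-sided 95% CI excludes 50% only at 7/7 (lower limit 59.0%; 6/7 gives 42.1%), and 0.9⁷ = 47.8%.

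**The case against.** **The figure is not a miscalculation.** It reproduces from a textbook formula. That stands; the fault is in relying on the formula at n = 10 and leaving the rule unstated.

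**Other readings accept 8/10 and so have 93.0% power.** One-sided 95% lower limits for 8/10 are 54.1% (Wilson), 53.3% (Agresti-Coull), 54.8% (Jeffreys) and 59.2% (Wald); only Clopper-Pearson, at 49.3%, just misses. A two-sided Wald interval also accepts it, and the one-sided mid-p value is 0.033. Taken literally, the sentence excludes rates below 50%, and at a true 49% the error of ≥ 8/10 is 4.80%. These readings are available because the protocol does not close them off. All of them are the same rule, however, and its error rises to 5.47% as the true rate approaches 50%. The stated power is attainable only by accepting that error, which the protocol does not say.

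**The excess over 5% is only 0.47 points, from discreteness, and n = 8 would meet the one-sided 5% standard.** Both are true. This should not be read as the trial being two patients short; 12 is the answer only at 2.5% per tail.

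**No planned analysis uses the figure.** This is the strongest point and it largely stands. The sample size was set by feasibility, the protocol's results are descriptive, efficacy will be pooled over two studies, and the SAP makes no power claim. It limits the weight of the point but does not make the sentence correct.

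**Conclusion.** The concern holds. With 10 patients no whole-number threshold gives 80% power at a 90% response rate with a true one-sided error of 5% or less. That result rests only on the binomial distribution and the protocol's 90% and 50% rates.

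The figure of 73.6% further assumes that excluding 50% means a two-sided 95% CI lying above it, by Clopper-Pearson, Wilson, Agresti-Coull or Jeffreys. On that reading the risk of missing a true 90% rate is 26.4%, against at most 20% as stated. The claim would be right if the protocol accepted a one-sided error of 5.47% or more, for example a 10% level, but it states no level. The sentence should be corrected, though its practical weight is low.

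**What to change.** Replace the power sentence in Protocol 16.1 and the synopsis, or record the point as a limitation in the study report, for example: *With 10 patients, at least 9 responders are needed for the exact two-sided 95% CI to exclude 50%; power is about 74% if the true rate is 90%.* If the sponsor meant another rule, state its alpha, sidedness, method and threshold.

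A minor addition: SAP 5.1.3 gives the responders with at least a 50% metHb reduction as a number and percentage, and specifies intervals only for means. Put an exact 95% CI beside the responder percentages, using the number actually analysed. That is at most 7 + 24 = 31 for the efficacy set, and possibly fewer in Table 14.2.1.1, which keeps only patients whose first post-dose metHb came before 2 hours.

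The cost is one sentence and one standard interval, with a slightly less favourable power statement. No extra patients and no change of analysis are needed.

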16.2. STATISTICAL METHODS

Statistical analyses will be performed by Orion under the authority of the Sponsor. Statistical analyses will be carried out using SAS®, Version 9.3 or later, SAS Institute, Cary, North Carolina, USA.

The statistical methods for this study, summarized below, will be described in a detailed statistical analysis plan (SAP), which will be finalized prior to database lock. Any deviations from the planned analysis as described in the SAP will be justified and recorded in the final clinical study report.

16.2.1. General Considerations

Continuous variables will be summarized by descriptive statistics (number of patients, mean, standard deviation [SD], minimum, median and maximum). Geometric mean and coefficient of variation (CV) will be presented for PK parameters when appropriate. Categorical data will be summarized by absolute and relative frequencies.

A 95% confidence interval (CI) for the responder rate will be presented for each of the primary and secondary endpoints.

All variables will be listed on a patient level.

Unless indicated otherwise, summary statistics will be reported for observed data only. Missing data will not be imputed. If a baseline value is missing, no change from baseline will be calculated.

Baseline for all assessments will be defined as the last measurement taken prior to dosing with study drug.

16.2.2. Analysis Sets

The following analysis sets will be analyzed:

Full Analysis Set (FAS)

The Full Analysis Set (FAS) is defined as all patients who are enrolled. The FAS will be used for all efficacy analyses.

Safety Set

The Safety Set is defined as all patients who receive at least one dose of ProvayBlueTM. The Safety Set will be used for all safety analyses.

PK Analysis Set

The PK Analysis Set is defined as those patients in the FAS who have any PK results.

